2.7.4 Other safety data

2.7.4.1 ECG and cardiac imaging data

The summary of ECG will only include treatment emergent data, which are defined as those ECG measurements after the first dose of study treatment and on or before last dose + 84 days.

Analysis in ECG parameters using descriptive summary statistics for the change from baseline for each post-baseline visit will be performed. These descriptive summaries will be presented by ECG parameter and treatment group. Change from baseline will only be summarized for subjects with both baseline and post-baseline values and will be calculated as:

Change from baseline = post-BSL - BSL

The following quantitative variables will be summarized: ECG mean heart rate, RR interval, PR interval, QRS duration, QT interval, and corrected QT interval (QTc). Fridericia (QTcF) corrections will be presented for QTc.

QTc will be summarized by computing the number and percentage of subjects (including 95% confidence intervals for pooled analysis, e.g. SCS) with:

- QTc > 500 msec
- QTc > 480 msec
- QTc > 450 msec
- QTc changes from baseline > 30 msec
- QTc changes from baseline > 60 msec
- PR > 250 msec

Summary statistics will be presented for ECG variables by visit and treatment group.

A listing of all newly occurring or worsening abnormalities will be provided, as well as a by-subject listing of all quantitative ECG parameters.

2.10 Patient-reported outcomes

Patient reported outcomes will be evaluated based on FAS unless otherwise specified.

BASDAI

The following variables will be evaluated:

- BASDAI
- BASDAI50

See Section 2.6 and Section 2.12 for details.

BASFI

See Section 2.6 and Section 2.12 for details.

Patient's global assessment of disease activity (VAS)

See Section 2.12 for details.

Patient's assessment of back pain intensity (VAS)

See Section 2.12 for details.

SF-36

The following variables will be evaluated:

- SF-36 domain scores (based on a scale of 0-100)
- SF-36 PCS and MCS scores (norm-based scores)
- SF-36 PCS and MCS responder (improvement of ≥ 2.5 points, [Lubeck, 2004](#))

See Section 2.6 and Section 2.12 for details.

While the SF-36 PCS score change from baseline is a secondary objective, the SF-36 MCS score, SF-36 domain scores and SF-36 PCS/MCS responder are not included in the objectives but will be presented as supportive information.

ASQoL

See Section 2.6 and Section 2.12 for details.

| Category | Value |
|----------|-------|
| 1 | ~0.2 |
| 2 | ~0.5 |
| 3 | ~1 |
| 4 | ~2 |
| 5 | ~5 |
| 6 | ~10 |
| 7 | ~15 |
| 8 | ~25 |
| 9 | ~35 |
| 10 | ~45 |
| 11 | ~55 |
| 12 | ~65 |
| 13 | ~75 |
| 14 | ~85 |
| 15 | 100 |

2.13 Interim analysis

No interim analysis will be performed.

2.14 Primary endpoint analysis

The primary endpoint analysis will be performed after all participants have completed the Week 16 visit or have discontinued earlier. The investigators, site personnel and monitors will continue to remain blinded to the original treatment assignment that each participant received at randomization until after the final database lock. The primary endpoint analysis will be used for regulatory submission.

Subsequent to the primary endpoint analysis, the final analysis is planned after participants have completed the Week F60 assessments and may be used for regulatory submission and/or publication purposes. Additional analyses may be performed to support interactions with health authorities, as necessary.

3 Sample size calculation

3.1 Primary endpoint(s)

As it is a bridging study for China registration, this study will pursue an estimation strategy rather than formal hypothesis testing of treatment difference.

Analysis of the phase III study CAIN457H2315 with secukinumab in nr-axSpA showed a placebo response rate of about 29.2% and a secukinumab 150 mg response rate of 41.5% after 16 weeks for ASAS40 in TNF- α naïve participants. Assuming 10% of randomized participants will be TNF- α IR and 90% of randomized participants will be TNF- α naïve. With 134 participants, 120 of them are TNF- α naïve (1:1 ratio to two groups), then there are approximately 77.3% probability to show at least 50% global treatment difference (6.15%) and approximately 90.7% probability to show positive treatment difference.

Table 3-1 Probability of Success with Different Observed Response Rates of ASAS40 in TNF- α naïve participants

| | Observed Response Rate | | | 95% CI of (p ₁ -p ₂) | Aimed Treatment Difference | Criterion 1 | | Criterion 2 | |
|------------|-------------------------------|---------------------------|--------------------------------|---|----------------------------|-------------|----------------------------|-------------|--|
| | Secukinumab (p ₁) | Placebo (p ₂) | p ₁ -p ₂ | | | PoS | Aimed Treatment Difference | PoS | |
| Scenario 1 | 0.395 | 0.292 | 0.103 | (-0.066, 0.272) | > 0.0615 | 0.699 | > 0 | 0.864 | |
| Scenario 2 | 0.415 | 0.292 | 0.123 | (-0.046, 0.293) | > 0.0615 | 0.773 | > 0 | 0.907 | |
| Scenario 3 | 0.435 | 0.292 | 0.143 | (-0.027, 0.313) | > 0.0615 | 0.835 | > 0 | 0.939 | |
| Scenario 4 | 0.455 | 0.292 | 0.163 | (-0.008, 0.334) | > 0.0615 | 0.885 | > 0 | 0.962 | |

4 Change to protocol specified analyses

Per protocol Section 12.4.4, ASAS40 response in active nr-axSpA participants at Week 16 was supposed to be evaluated using a non-parametric regression model as a “sensitivity analysis”. This analysis has been removed (SAP Section 2.5.4), considering the non-parametric regression model will target the odds ratio, while the primary estimand targets the marginal difference as the summary measurement. Additionally, no evidence for lack of robustness was identified from the global pivotal study CAIN457H2315.

Per protocol Section 12.5.2, Qualitative changes of ECG were supposed to be summarized. But the qualitative changes (interpretation) of ECG were not collected in CRF and hence will not be analyzed (SAP Section 2.7.4.1).

5 Appendix

5.1 Description of efficacy variables

Assessment of SpondyloArthritis International Society criteria (ASAS)

The ASAS response measures consist of the following assessment domains ([Sieper et al 2009](#)).

Main ASAS domains:

1. Patient's global assessment of disease activity measured on a VAS scale
2. Patient's assessment of back pain, represented by either total or nocturnal pain scores, both measured on a VAS scale
3. Function represented by BASFI average of 10 questions regarding ability to perform specific tasks as measured by VAS scale
4. Inflammation represented by mean duration and severity of morning stiffness, represented by the average of the last 2 questions on the 6-question BASDAI as measured by VAS scale

Additional assessment domains:

5. Spinal mobility represented by the BASMI lateral spinal flexion assessment
6. C-reactive protein (acute phase reactant)

ASAS Response Criteria-20% (ASAS20)

ASAS20 response is defined as an improvement of $\geq 20\%$ and ≥ 1 unit on a scale of 10 in at least three of the four main domains and no worsening of $\geq 20\%$ and ≥ 1 unit on a scale of 10 in the remaining domain with non-zero baseline assessment, or no worsening of ≥ 1 unit on a scale of 10 in the remaining domain with zero baseline assessment.

ASAS Response Criteria-40% (ASAS40)

ASAS40 response is defined as an improvement of $\geq 40\%$ and ≥ 2 units on a scale of 10 in at least three of the four main domains and no worsening at all in the remaining domain.

ASAS 5/6 improvement criteria

The ASAS 5/6 improvement is defined as an improvement of $\geq 20\%$ in at least five of all six domains.

ASAS partial remission criteria

The ASAS partial remission criteria are defined as a value not above 2 units in each of the four main domains on a scale of 10.

ASAS components

Patient's global assessment of disease activity (VAS)

The patient's global assessment of disease activity will be performed using a 100 mm visual analog scale (VAS) ranging from not severe to very severe, after the question, "*How active was your disease on average during the last week?*"

Patient's assessment of total back pain and nocturnal back pain intensity (VAS)

The patient's assessment of back pain will be performed using a 100 mm VAS ranging from no pain to unbearable pain, after the question "*Based on your assessment, please indicate what is the amount of back pain at any time that you experienced during the last week?*" and "*Based on your assessment, please indicate what is the amount of back pain at night that you experienced during the last week?*"

Bath Ankylosing Spondylitis Functional Index (BASFI)

The BASFI is a set of 10 questions designed to determine the degree of functional limitation in those participants with AS. The ten questions were chosen with a major input from participants with AS. The first 8 questions consider activities related to functional anatomy. The final 2 questions assess the participants' ability to cope with everyday life. A 10 cm visual analog scale is used to answer the questions. The mean of the ten scales gives the BASFI score – a value between 0 and 10. In the case that some of the BASFI questions are missing, then the average of the non-missing items is used (Braun 2009, van Tubergen 2001).

[figure not shown]
Bath Ankylosing Spondylitis Disease Activity Index (BASDAI)

The BASDAI consists of a 0 through 10 scale (0 being no problem and 10 being the worst problem, captured as a continuous VAS), which is used to answer 6 questions pertaining to the 5 major symptoms of AS:

1. Fatigue
2. Spinal pain
3. Joint pain / swelling
4. Areas of localized tenderness
5. Morning stiffness severity
6. Morning stiffness duration

To give each symptom equal weighting, the mean (average) of the two scores relating to morning stiffness is taken and is then added to the sum of the first 4 questions. The resulting 0 to 50 score is divided by 5 to give a final 0 – 10 BASDAI score. Scores of 4 or greater suggest suboptimal control of disease, and subjects with scores of 4 or greater are usually good

candidates for either a change in their medical therapy or for enrollment in clinical trials evaluating new drug therapies directed at AS. BASDAI is a quick and simple index taking between 30 secs and 2 mins to complete. At least 4 questions should be non-missing to calculate the BASDAI score. Otherwise, BASDAI score will be missing (Haywood 2002). If both Q5 and Q6 are missing or one of Q1 to Q4 is missing, then the total sum should be divided by 4 instead of 5. If two of Q1 to Q4 is missing and both Q5 and Q6 are not missing, then the sum should be divided by 3.

High sensitivity C-reactive protein (hsCRP)

This assessment will be performed in order to identify the presence of inflammation, to determine its severity, and to monitor response to treatment.

Since the results of this test may unblind study personnel, results from the central lab will be provided for screening and baseline only. The hsCRP results from samples collected during the treatment period will be revealed following database lock only.

[figure not shown]
Definition of Sacroiliitis on MRI

An MRI will be considered positive for sacroiliitis (active inflammatory lesions, “positive MRI”, MRI+) if the following characteristics are evident ([Sieper et al 2009](#)):

- The presence of definite subchondral bone marrow oedema/osteitis highly suggestive of sacroiliitis is mandatory.
- The presence of synovitis, capsulitis, or enthesitis only without concomitant subchondral bone marrow oedema/osteitis is compatible with sacroiliitis but not sufficient for making a diagnosis of active sacroiliitis.

Amount of signal required: if there is one signal (lesion) only, this should be present on at least two slices. If there is more than one signal on a single slice, one slice may be enough.

[REDACTED]

[REDACTED]

[REDACTED]

[REDACTED]

[REDACTED]

[REDACTED]

[REDACTED]

5.2 Description of health-related quality of life variables

5.2.1 SF-36

The Short Form Health Survey (SF-36) is a widely used and extensively studied instrument to measure health-related quality of life among healthy subjects and patients with acute and chronic conditions. It consists of eight subscales (domains) that can be scored individually: Physical Functioning, Role-Physical, Bodily Pain, General Health, Vitality, Social Functioning, Role- Emotional, and Mental Health. Two overall summary scores, the Physical Component Summary (PCS) and the Mental Component Summary (MCS) also can be computed. The SF-36 has proven useful in monitoring general and specific populations, comparing the relative burden of different disease, differentiating the health benefits produced by different treatments, and in screening individual patients. The eight domains are based on a scale from 0-100 while PCS and MCS are norm-based scores with a mean of 50 and a standard deviation of 10.

Quality metric uses weighted maximum likelihood estimation, a modified version of item response theory (IRT) to estimate scale scores when a respondent is missing multiple items. The PCS summary score measure requires scores for seven scales, one of which must be the PF scale and the MCS score also requires scores for seven scales, one of which must be the MH scale. Only one item is needed for each of the multi-item domains.

5.2.2 Ankylosing Spondylitis Quality of Life (ASQoL)

The ASQoL is a self-administered questionnaire designed to assess health-related quality of life in adult patients with Ankylosing Spondylitis. The ASQoL contains 18 items with a dichotomous yes/no response option. A single point is assigned for each “yes” response and no points for each “no” response resulting in overall scores that range from 0 (least severity) to 18 (highest severity). As such, lower score indicates better quality of life. Items include an assessment of mobility/energy, self-care and mood/emotion. The recall period is “at the moment,” and the measure requires approximately 6 minutes to complete.

At least 15 answered questions are required to be able to calculate ASQoL using mean imputation, (sum of answered) / (number answered) * 18 ([Doward 2003](#)).

5.3 Imputation rules

5.3.1 Study drug

Any partial dates will be imputed as follows:

We take the earlier day of

- The last day in the month and
- The end day of the corresponding epoch

5.3.2 AE date imputation

Impute AE end date:

1. If the AE end date ‘month’ is missing, the imputed end date should be set to the earliest of the (min (last visit date, last dose date + 84 days), 31DECYYYY, date of death).
2. If the AE end date ‘day’ is missing, the imputed end date should be set to the earliest of the (min (last visit date, last dose date + 84 days), last day of the month, date of death)
3. If AE ‘year’ is missing or AE is ongoing, the end date will not be imputed.

Impute AE start date:

Before imputing AE start date, find the AE start reference date.

1. If the (imputed) AE end date is complete and the (imputed) AE end date < treatment start date then AE start reference date = min(informed consent date, earliest visit date).
2. Else AE start reference date = treatment start date
 1. If the AE start date ‘year’ value is missing, the date uncertainty is too high to impute a rational date. Therefore, if the AE year value is missing, the imputed AE start date is set to NULL.
 2. If the AE start date ‘year’ value is less than the treatment start date year value, the AE started before treatment. Therefore:
 - a. If AE ‘month’ is missing, the imputed AE start date is set to the mid-year point (01JulYYYY).

- b. Else if AE 'month' is not missing, the imputed AE start date is set to the mid-month point (15MONYYYY).
3. If the AE start date year value is greater than the treatment start date year value, the AE started after treatment. Therefore:
 - a. If the AE month is missing, the imputed AE start date is set to the year start point (01JanYYYY).
 - b. Else if the AE month is not missing, the imputed AE start date is set to the later of (month start point (01MONYYYY), AE start reference date + 1 day).
4. If the AE start date year value is equal to the treatment start date year value:
 - a. And the AE month is missing the imputed AE start date is set to the AE reference start date + 1 day.
 - b. Else if the AE month is less than the treatment start month, the imputed AE start date is set to the mid-month point (15MONYYYY).
 - c. Else if the AE month is equal to the treatment start date month or greater than the treatment start date month, the imputed AE start date is set to the later of (month start point (01MONYYYY), AE start reference date + 1 day).

If complete (imputed) AE end date is available and the imputed AE start date is greater than the (imputed) AE end date, then imputed AE start date should be set to the (imputed) AE end date.

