2.1.1 General definitions

2.1.1.1 Treatment groups

The summaries by treatment will be performed by the randomized treatment or treatment sequence.

- Randomized treatment:
 - AIN457 150 mg s.c.
 - Placebo s.c.
- Treatment sequence:
 - AIN457 150 mg
 - AIN457 150 mg – AIN457 300 mg
 - Placebo
 - Placebo – AIN457 150 mg
 - Placebo – AIN457 150 mg – AIN457 300 mg

For some safety summaries (e.g. exposure-adjusted) the ‘switch’ treatment may be summarized separately:

Week 1 – Week 16: AIN457 150 mg, Placebo

Entire study: Any AIN457 150 mg, Any AIN457 300 mg, Any AIN457, Placebo

Unless otherwise specified, at the primary endpoint analysis, efficacy data for the placebo-controlled period and safety data up to Week 16 and Entire study will be presented. Additional aspects of efficacy, safety and tolerability of secukinumab will be investigated in the final analysis. Additional analyses may also be performed to support interactions with health authorities, as necessary.

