2.4 Treatments (study treatment, rescue medication, concomitant therapies, compliance)

2.4.1 Study treatment / compliance

The analysis of study treatment data will be based on the safety set. The number of active and placebo injections will be presented by treatment group.

The duration of exposure to study treatment will also be summarized by treatment group. In addition, the number and percentage of participants with cumulative exposure levels (e.g. any exposure, ≥ 1 week, ≥ 2 weeks ≥ 3 weeks, ≥ 4 weeks, ≥ 8 weeks, etc.) will be presented.

Duration of exposure is defined as the time from first dose of study treatment to the time of treatment switch (for participants who switch treatment) or minimum of (last dose of the treatment + 84 days) and (last visit date). Participants who switch treatment during the study (e.g. from placebo to active treatment) will have exposure to both medications using the appropriate start and stop dates.

Duration of exposure (years) = duration of exposure (days) / 365.25

Duration of exposure (100 subject years) = duration of exposure (years) / 100

The analysis of duration of exposure described above will be done for the entire study treatment period.

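### Partial AE start dates ignore treatment changes, so entire-study safety tables credit ambiguous AEs to the earlier treatment

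*SAP*

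**What the plan says.** SAP 5.3.2 first sets a reference date. Unless the AE ended before treatment began, the rule is "Else AE start reference date = treatment start date". The start date is then completed as follows.

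- Day missing, in the first-dose month or later: "the imputed AE start date is set to the later of (month start point (01MONYYYY), AE start reference date + 1 day".
- Month missing, same year as first dose: "And the AE month is missing the imputed AE start date is set to the AE reference start date + 1 day".
- Month missing, later year: "the imputed AE start date is set to the year start point (01JanYYYY".
- Override: if "the imputed AE start date is greater than the (imputed) AE end date", the start is moved to the end date.

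The remaining branches cover starts before treatment (mid-month or mid-year) and a missing year (no imputation). Neither bears on treatment changes.

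Elsewhere, the SAP makes the event date decide the column. Section 1.1 moves all placebo participants to secukinumab 150 mg at Week 16 and escalates ASAS20 non-responders to 300 mg at Week 24. Section 2.1.1.1 lists the columns "Entire study: Any AIN457 150 mg, Any AIN457 300 mg, Any AIN457, Placebo". Under section 2.4.1, participants who switch "will have exposure to both medications using the appropriate start and stop dates". Table 5-3 in section 5.5.3.1 assigns each event by its study day relative to the switch. Section 2.7.1 adds that date-imputation algorithms will be given in a Programming Datasets Specification, which is not among the documents.

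**The concern.** The rule takes the earliest post-first-dose date that fits what was recorded. At first dose this is cautious: an ambiguous AE in that month becomes treatment-emergent. At the Week 16 change the same formula works the other way, because the earlier side is placebo. An AE that might have begun on secukinumab is dated back to placebo, while one that began on placebo is never dated forward. In a safety summary that sets Placebo beside Any AIN457, this raises the placebo rate and lowers the secukinumab rate, which is the anti-conservative direction. At Week 24 the same gap moves AEs from 300 mg to 150 mg.

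The SAP recognises the problem for by-visit values: Table 2-2 states which side of the placebo-to-secukinumab switch a measurement is taken from. It has no counterpart for AE dates.

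**Working it through.** **The plan's own example.** Table 5-3 has 100 placebo days and an event on Day 110. 110 − 100 = 10 days into 150 mg, as printed. Attribution therefore follows the event day.

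**Worked dates** (Week 16 target day is Day 113, Table 2-1).
- First dose 1 March 2022, switch 21 June 2022. An AE recorded as June 2022 becomes 1 June (Day 93, placebo). One recorded as July 2022 becomes 1 July (secukinumab). One recorded only as 2022 becomes 2 March (placebo).
- First dose 1 October 2022, switch 21 January 2023. An AE recorded only as 2023 becomes 1 January 2023 (placebo).
- First dose 1 August 2022, switch 21 November 2022. An AE recorded only as 2023 becomes 1 January 2023, which is already on secukinumab.

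**Share moved.** The 5.3.2 rules were applied to 1,461 consecutive first-dose dates from 1 March 2021, with the switch on Day 113. Onset was assumed uniform over days. The table gives the share of true on-secukinumab onsets in placebo-arm participants that are dated to placebo.

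| True onset after the switch | Day missing | Month missing |
|---|---|---|
| First 14 days | 75.4% | 97.9% |
| First 30 days | 49.1% | 95.8% |
| Up to Week 24 | 26.3% | 92.2% |
| Up to Week 60 | 4.8% | 57.6% |

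Among day-missing onsets on or after the switch and within the switch month, 21,520 of 22,981 (93.6%) are moved. The rest arise only when the switch falls on the 1st (3.3% of first-dose dates). The reverse error, a true placebo onset dated to secukinumab, is 0% throughout, because the imputed date is never later than the true one.

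**Chance that a switch-month AE is truly on secukinumab.** For switch day d in a 30-day month this is (30 − d + 1)/30. That gives 26/30 = 87% for d = 5, 16/30 = 53% for d = 15 and 6/30 = 20% for d = 25.

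**Effect of one moved event.** With 134 randomised 1:1 there are 67 per arm. Full follow-up runs to Week 60 (420 days, of which 308 follow the switch).
- Placebo exposure: 67 × 112/365.25 = 20.5 patient-years; 100/20.5 = 4.9 per 100 patient-years.
- Any AIN457 exposure: 67 × (420 + 308)/365.25 = 133.5 patient-years; 100/133.5 = 0.75 per 100 patient-years.

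Both hold person-time fixed, so they suit infrequent events. Section 5.5.3.1 counts participants with at least one event, so they apply only to a first occurrence.

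**Aggregate.** The share of AEs lacking the day is not given. Assuming 1% to 10%, 0.01 × 4.8% = 0.05% to 0.10 × 4.8% = 0.5% of placebo-arm participants' on-secukinumab AEs would move.

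**A later-side rule.** If day-missing AEs in the switch month are instead placed on the later side, none move from secukinumab to placebo. However, 21,520 of 162,171 (13.3%) true placebo onsets (Days 2 to 112) move to secukinumab. That is the same count of onset days as the present rule misplaces, in the opposite direction.

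**The case against.** The strongest reply concerns the randomised period. A reader might infer that the Week 16 safety comparison is tilted towards secukinumab; the documents do not support that. Table 2-3 plans crude incidence for Day 1 to Week 16, and there the rule pulls early post-Week 16 AEs back into the window in both arms, each into its own column. The one-way shift belongs to the entire-study columns, which set about 16 weeks of placebo beside up to 60 weeks of secukinumab and are not a randomised contrast. At Week 24 both doses fall under Any AIN457, so Placebo versus Any AIN457 is unaffected there. All of this stands and limits the point.

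Partial dates should also be uncommon. The protocol asks about AEs at every visit, records start and end dates, and queries missing values (sections 10.1.1 and 11.2). This stands as a reason to expect a small effect, although neither document gives a count.

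The Programming Datasets Specification might contain a switch rule. That possibility remains, but 5.3.2 already sets out a complete algorithm without one. A specification that added one would differ from the SAP and would need reconciling.

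Finally, a later-side rule exchanges one systematic error for another. That is true, and it is why both assignments should be reported.

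**Conclusion.** The point holds for the entire-study by-treatment summaries. An AE whose partial start date spans a participant's own treatment change is almost always credited to the earlier treatment (placebo, or 150 mg before escalation) and never the reverse. The direction follows from the written rule. The percentages rest on uniform onset and a Day 113 switch; the rate effects rest on full follow-up and a first occurrence.

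Two stronger readings should be resisted. First, not every partial date goes to placebo: with only the day missing, an AE recorded in the month after the switch is dated to secukinumab. Second, a moved AE does not always add 4.9 per 100 patient-years; it adds nothing to the placebo numerator if that participant already had the event on placebo. The aggregate distortion is probably small, with rates for infrequent events the most sensitive. The SAP should still be corrected, because the bias is one-sided and the remedy is cheap.

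**What to change.** Add to SAP 5.3.2 a rule that applies only to entire-study by-treatment summaries and only to participants who actually change treatment (placebo to 150 mg at Week 16; 150 mg to 300 mg at Week 24):

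- If the known part of the start date fits both sides of the change, attribute the AE to the later treatment by imputing the day after that dose, unless the AE end date is earlier.
- If it spans both changes, state which one governs, for example the placebo-to-secukinumab change for Placebo versus Any AIN457.
- Keep the Day 1 to Week 16 randomised summary under one identical rule in both arms. The secukinumab arm has no treatment change at Week 16, and moving its AEs past that date would remove them from its own column.
- Report the number of affected AEs and the rates under the opposite assignment.
- Align the Programming Datasets Specification with this text.

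The cost is a short SAP addition and a small change to the derivation, with no new data. The downside is that some true placebo AEs (about 13% of day-missing ones in the check above) would be attributed to secukinumab. That is the conservative direction for Placebo versus Any AIN457, and the two-way report makes it visible.
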